## 5. MILESTONES

In order to obtain enough information to perform a proper analysis of the data, the proposed work plan is as follows:

Once the study is approved by the competent authorities and the contracts have been signed at each site, each study site will be opened and the investigator may start recording the requested data in the electronic case report form.

Before including the patient in the study, the investigator should review and verify the inclusion/exclusion criteria.

The observation period—given that it is an observational, retrospective study—will always be prior to the inclusion of the patient in the study, with this starting at the time of diagnosis of the study condition (renal cell carcinoma) and ending at the time of inclusion in the study, or the death of the patient if this occurs first.

[figure not shown]
The person appointed by the sponsor to monitor the study may request a face-to-face or remote visit from the site for the review of the data reported in the eCRF at any time after the first patient is included.

The site undertakes to fill in the data in the CRFs, and to resolve any discrepancies that may arise in them, on a regular basis and without interfering with the study’s planned schedule.

The study sponsor will regularly inform the investigators involved in the study on its status by sending electronic monitoring reports.

The administrative procedures for the study with the central IEC and the AEMPS are expected to start in September/October 2017, so the following schedule is being considered:

Milestone	Expected date
Date of approval from the central IEC	7 NOVEMBER 2017
Start of data collection Date of opening of the first site and start of study recruitment	15 MARCH 2018
End of recruitment period Expected date of study recruitment closure	30 SEPTEMBER 2018
End of data collection	30 DECEMBER 2018

Expected date of closing of study data collection	
Final results report Expected date for the final results of the study	31 MARCH 2019

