### **9.1. Patient information and consent**

All parties will ensure that personal data are protected and will not include patients’ names on any of the sponsor’s forms, reports, publications or any other text for disclosure, unless so required by law. For data transfer, Pfizer will maintain a high level of confidentiality and protection of patients’ personal data.

Since this study is retrospective, a large number of patients will probably have died by the time they are included. In this case, and in accordance with order SAS/3470/2009 of 16 December on observational post-authorisation studies in which it is established that “In studies that require subjects to be interviewed or in those in which, using other sources of data, it is not possible to use a safe dissociation procedure that ensures that the information contains no personal data, subjects must be asked to provide informed consent, which must be granted in writing in accordance with current regulations”, these patients will not be required to provide their signed informed consent. In the case of patients who are alive at the time of their inclusion in the study, the informed consent form must comply with the routine regulatory requirements, which should comply with ICH GCP, local administrative standards and legal requirements.

The informed consent form used in this study and any changes made during the course of the study must be prospectively approved by the IEC and by Pfizer prior to implementation.

The investigator must ensure that each study patient or his/her legal representative is informed of the nature and objectives of the study and possible risks associated with his/her participation therein. The investigator, or a person appointed by the same, will obtain written informed consent from each patient or his/her legal representative before performing any study-specific procedure. The investigator will retain the original of each patient’s signed informed consent form.

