**Analysis population****All analyses will be performed with evaluable patients.**

The CRF contains the information related to the eligibility criteria as binary variable (Yes/No) for each of the described items.

Several of these criteria can be verified with the data recorded in the CRF. This verification is performed in order to prevent the inclusion of non-evaluable participants in the statistical report and prior to the start of any analysis.

These patients will be considered screening failure, and in the statistical report they will thus be included in a table of patient disposition together with the patients screening failure initially confirmed by the sponsor.

The criteria to be verified in the patient CRFs to define the evaluable population are described below:

- An "evaluable" patient must have received at least one dose of axitinib prior to inclusion in the study: it must be verified that the "Starting dose" and the "Treatment start date with axitinib" have been specified in "Treatment with axitinib". This date must be prior to the date of signing the informed consent (for patients who are still alive at enrolment).

- Inclusion requirement *Patients must have received axitinib as second-line treatment or further line*: it must be verified that there is information concerning a first-line treatment in the "First-line treatment" section.

- IC1: *Evidence of a personally signed and dated informed consent document indicating that the patient (or his/her legal representative) has been informed of all relevant aspects of the study. Informed consent will only be obtained from patients who are still alive.*

It must be verified that the date of signing the informed consent is specified (for patients who are still alive at enrolment).

Noted that for patients already dead before the study inclusion, the CII could be "No".

- IC2: *Aged 18 or over.*

It must be verified that the age calculated with respect to the date of the baseline visit is  $\geq 18$  years.

- IC3: *Histologically confirmed diagnosis of advanced renal cell carcinoma, with at least one radiological evaluation of the disease according to RECIST 1.1 criteria.*

It must be verified that the following data have been indicated: Date of first diagnosis, Tumour stage at disease diagnosis, Date of advanced disease diagnosis, Stage of advanced disease, Metastasis location, Best treatment response (first-line treatment).

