## 7 DEFINITION OF VARIABLES AND OBJECTIVES

In addition, the following variables will be calculated from the CRF data:

NOTE: In patients with dates after the date of the IC visit / signature, the date of the IC visit / signature has been considered as the date of the last check. Due to the retrospective nature of the study, no data can be collected after the patient was included in the IC study / signature.

- Age (years) of patient at time of visit= (Visit date – Date of birth) / 365.25
- Age (years) at first diagnosis= (Date of first diagnosis – Date of birth) / 365.25
- Age (years) at the initiation of axitinib= (start date of axitinib – Date of birth) / 365.25
- Number of metastatic locations = sum (Lymph nodes, CNS, Hepatic, Pulmonary, Bone, Other).
- • Neutrophil / lymphocyte ratio. It will be categorized as follows:  $\leq 3$ ,  $> 3$ . "Before the beginning of the first line" and "At the beginning of treatment with axitinib" will be analyzed. This ratio is not calculated on axitinib suspension because there is no current lymphocyte value data in that part of the CRF.
- Time (months) between first diagnosis and nephrectomy = (Date of nephrectomy – Date of first diagnosis) / 30.4375. A list with the information (site, patient, date of first diagnosis, date of nephrectomy and the calculated time) in cases in which the time is negative (with date of nephrectomy before or equal to date of first diagnosis) will be displayed, and these cases will not be included in the descriptive analysis
- Time (months) between first diagnosis and radiotherapy = (Date of radiotherapy – Date of first diagnosis) / 30.4375. A list with the information (site, patient, date of first diagnosis, date of radiotherapy and the calculated time) in cases in which the time is negative (with date of radiotherapy before or equal to date of first diagnosis) will be displayed, and these cases will not be included in the descriptive analysis.
- Time (months) between first diagnosis and 1st-line treatment = (Date of the initiation of 1st-line treatment – Date of first diagnosis) / 30.4375. A list with the information (site, patient, date of first diagnosis, date of 1st-line treatment and the calculated time) in cases in which the time is negative (with date of 1st-line treatment before or equal to date of first diagnosis) will be displayed, and these cases will not be included in the descriptive analysis

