## 7.1 PRIMARY OBJECTIVE

In order to meet the study's primary objective, the baseline clinical characteristics of two patient groups with extreme response to the drug will be compared: A group of patients with long-term responses to the drug (long-term responders to axitinib) versus a group of patients with disease progression at the first assessment after the initiation of treatment (group of patients refractory to axitinib).

The classification (in long-term responders or refractory patients) will be based on PFS (in months), as indicated in section 5.2.

It will be shown the following descriptive tables:

- “Long responder” patient (Yes, No). “Long responding patient” is defined if he / she has an PFS  $\geq 9$  months (during axitinib treatment). The 95% CI will be displayed.
- PFS in long responding patients. Only the descriptive analysis of the time in months and the CI for the average, will be shown.
- “Refractory” patient (Yes, No). "Refractory patient" is defined if there is a better response to treatment = PE (to axitinib treatment). 95% CI will be shown.
- PFS in refractory patients. Only the descriptive analysis of the time in months and the CI for the average will be shown.
- Patient group (Long respondent, refractory). It is defined in section 5.2. IC95% will be displayed

At the same time, In addition to comparisons of baseline clinical characteristics between the groups (long-term responders, refractory patients), an association analysis of the following factors with the study groups will be performed:

- Age with respect to first visit ( $\leq 65$  years and  $> 65$  years).
- Age with respect to first diagnosis ( $\leq 65$  years and  $> 65$  years).
- Age with respect to start of axitinib ( $\leq 65$  years and  $> 65$  years).
- Baseline ECOG/PS and at the initiation of first line treatment (0, 1 and  $\geq 2$ ).
- Baseline ECOG/PS and at the initiation axitinib treatment (0, 1 and  $\geq 2$ ).
- Baseline ECOG/PS and at the end of axitinib treatment (0, 1 and  $\geq 2$ ).
- Number of previous treatment lines
- Number of previous treatment lines (1, 2 and  $\geq 3$ )
- Previous nephrectomy (yes and no)
- MSKCC (or IMDC) risk group in all moments in which it is analysed during the study (favourable, intermediate and poor)

- Histology (100% clear cells, primarily clear cells, primarily non-clear cells, 100% non-clear cells)
- Duration of first-line treatment

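### Age at the study visit is tested against response group in the primary comparison, although that visit comes after the axitinib outcome and has no defined date for patients who have already died

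*SAP*

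**What the plan says.** SAP section 7 derives three ages. One runs to the visit: "Age (years) of patient at time of visit= (Visit date – Date of birth) / 365.25". The other two run to first diagnosis and to the start of axitinib. SAP section 7.1 enters all three, each split at 65 years, in the list of factors to be associated with response group; the first entry is "Age with respect to first visit". Protocol section 7.1 lists a single age factor with the same cut and gives no reference date.

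The documents never define the visit on its own. The note that opens SAP section 7 equates it with consent: for records dated later, "the date of the IC visit / signature has been considered as the date of the last check". Consent is taken only from living patients. Protocol section 9.1 expects that "a large number of patients will probably have died by the time they are included". Protocol section 5 has the observation period "ending at the time of inclusion in the study, or the death of the patient if this occurs first", with recruitment planned from 15 March to "30 SEPTEMBER 2018".

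The eligibility check on adult age in SAP section 2.1 uses the same kind of date: "It must be verified that the age calculated with respect to the date of the baseline visit is" at least 18 years.

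**The concern.** The primary objective looks for clinical factors related to long-term response. An age fixed at inclusion does not describe the patient when axitinib was started. It equals age at axitinib start plus the time from that start to inclusion, and the second part reflects when the site treated the patient and when the study opened. If that lag differs between long responders and refractory patients, the table shows an age difference even where the groups were equally old at treatment.

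Deceased patients add a second problem. If the data-entry or inclusion date is used for them, the formula returns an age they never reached, at a time outside the protocol's observation period. If the field is left blank, the factor is missing for the dead and the comparison covers survivors only, although survival is itself related to the outcome that defines the groups.

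At stake is a p-value for age in the primary comparison, unadjusted for multiplicity (SAP sections 4 and 9.1), that could be read as an association between age and benefit.

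**Working it through.** The plan states no figure on this point, so there is nothing to reproduce. Four checks follow.

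**1. Possible length of the lag.** Protocol section 6.1.4 gives EMA authorisation on 3 September 2012 and Spanish authorisation on 1 June 2014. Up to the planned close of recruitment on 30 September 2018:
- from the EMA date: 2,218 days / 365.25 = 6.1 years
- from the Spanish date: 1,582 days / 365.25 = 4.3 years

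These are upper limits. The documents give no typical lag.

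**2. The SAP formula applied to a deceased patient.** Take an invented patient born 1 January 1951 who starts axitinib on 1 June 2014 and dies on 1 December 2014. Assume the inclusion date, 30 June 2018, is entered as the visit date.
- age at axitinib start: 23,162 / 365.25 = 63.4
- age at death: 23,345 / 365.25 = 63.9
- age at visit: 24,652 / 365.25 = 67.5

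The patient is placed above 65 without having reached it. This result depends on the assumption about the date entered.

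**3. Total movement across the cut.** Assume age at axitinib start is normal with mean 64 (the median age at diagnosis in Protocol section 6.1.1, used as a stand-in) and SD 10 to 12, which the documents do not give. The share moved from at most 65 to over 65 by a lag L is Φ((65 − 64)/SD) − Φ((65 − L − 64)/SD).

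| Lag | SD 10 | SD 12 | Patients in 60 |
|---|---|---|---|
| 2 years | 8.0% | 6.6% | 4 to 5 |
| 4 years | 15.8% | 13.2% | 8 to 9 |

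This counts misplaced patients. It is not bias between groups, because a lag common to both groups moves both alike.

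**4. Between-group difference caused by lag alone.** Give both groups the same true ages. The share over 65 at lag L is 1 − Φ((65 − L − 64)/SD).

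*Shortest lags.* A long responder has at least 9 months from axitinib start to inclusion. A refractory patient's first assessment is put at 3 months or less; take 2.5 months as an assumption. The difference is 6.5 months.
- SD 10: 49.0% − 46.9% = 2.2 points (from unrounded shares)
- SD 12: 49.2% − 47.4% = 1.8 points

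With 60 patients in the 2:1 ratio that the protocol abstract expects, there are about 20 refractory patients, and 0.02 × 20 = 0.4 of a patient.

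*Lags that differ by years* (mean 64, SD 11, purely illustrative):
- 2 versus 4 years: 54% versus 61% over 65, odds ratio 0.75
- 1 versus 5 years: 50% versus 64%, odds ratio 0.56

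With no lag, both groups would show 46%. Exchanging the lags between the groups reverses the direction.

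**The case against.** The strongest reply is that the plan already contains the right analysis. Age at axitinib start, with the same cut, stands in the same list, and SAP section 7.1 admits to the logistic model only factors that precede axitinib. Visit age is then one labelled, unadjusted row in an exploratory study. The list is also not confined to baseline items: it includes response, axitinib duration and vital status. Protocol section 8.7 allows the SAP to modify the plan, so three ages in place of one is not in itself a contradiction. All of this stands, and it is why the point is minor. SAP sections 9.1 and 9.2 describe the logistic regression without repeating the restriction, but both refer back to section 7.1, which states it.

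A reader might infer that the plan certainly assigns ages to the dead that they never reached. The documents do not establish this. They define no visit date for a deceased patient, and the field could equally be left blank. The defect holds either way, but its form is unknown.

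A reader might also take the 7 to 16% in check 3 as the bias. It is total movement across the cut, under an assumed SD and lag.

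Nor does a patient's own survival enter an age that runs on past death. Survival matters only if the dead are missing from the factor.

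Finally, the eligibility check might look like a second serious error. It could admit only someone under 18 at axitinib start and 18 or over at inclusion. The indication is for adults, and use outside the product characteristics is an exclusion, so the effect is negligible.

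**Conclusion.** The point holds and is minor. Visit age is fixed after the axitinib outcome, has no defined reference date for a group that the protocol expects to be large, and mixes age with calendar time. It should not be tested as a factor in the primary comparison. The consequence is one extra, potentially misleading unadjusted comparison; the prognostic model and the analysis of age at axitinib start are unaffected.

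The documents do not allow the bias to be sized, because they give no lag by group. The illustrations rest on a normal age distribution, a centre borrowed from age at diagnosis, and an assumed SD. On that basis, the 6.5-month difference between the shortest lags is worth about 2 percentage points in the share over 65. Lags that differ by 2 to 4 years would be worth about 7 to 14 points at SD 11. The direction is unknown.

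**What to change.** In SAP section 7.1, delete the visit-age entry from the factor list and from the group tests. Name age at axitinib start as the single primary age factor and keep age at first diagnosis as descriptive. If age at inclusion is shown at all, show it descriptively for patients alive at inclusion.

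Optionally, base the adult-age check in SAP section 2.1 on age at axitinib start. This is a tidy-up and is unlikely to change any patient's eligibility.

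The cost is SAP wording and the removal of one table row. Age at axitinib start is already derived in section 7, so no new data are needed.

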    - Has treatment with axitinib been discontinued? (Yes/No)
      - If yes, specify:
        - End-of-treatment date
        - Reason for suspension of treatment (DP/Toxicity/Other, specify)
    - Risk criteria at discontinuation of treatment with axitinib

- 
- Time from first diagnosis to systemic treatment less than 1 year (Yes/No/Unknown)
    - ECOG/PS (current status) (Yes/No/Unknown)
    - LDH >1.5 x ULN (Yes/No/Unknown)
    - Haemoglobin < LLN (Yes/No/Unknown)
    - Corrected calcium >10 mg/dl (Yes/No/Unknown)
    - Presence of 2 or more metastatic sites (Yes/No/Unknown)
    - Platelets > ULN (Yes/No/Unknown)
    - Neutrophils > ULN (Yes/No/Unknown) (value)
  - Has there been disease progression? (No/Yes, specify date)
  - Best treatment response (CR, PR, SD, DP/Not evaluable).
    - Date of the best response obtained
  - Starting dose (5 mg/12 h; 2 mg/12 h; 3 mg/12 h; 7 mg/12 h; 10 mg/12 h)
  - Has the dose been modified? (Yes/No)
    - If yes, specify:
      - Increased/Reduced
      - Dose modification date
      - Reason for dose modification
      - New dose (5 mg/12 h; 2 mg/12 h; 3 mg/12 h; 7 mg/12 h; 10 mg/12 h; other, specify mg/h)
  - Adverse events
    - Adverse events (Anaemia; Asthenia; Fatigue; Diarrhoea; Dysphonia; Elevated ALT/GPT; Elevated AST/GOT; Elevated Bilirubin; Elevated Creatinine; Elevated Haemoglobin; Elevated Lipase; Hypercalcaemia; Hypertension; Hypocalcaemia; Hypophosphatemia; Hypothyroidism; Lymphopenia; Mucositis; Nausea; Neutropenia; Proteinuria; Rash; Hand-foot syndrome; Thrombocytopenia; Vomiting, Other, specify).
    - Worst grade according to CTCAE
    - Cycle in which the worst grade occurred
    - Related to treatment (Yes/No)
    - Serious AE? (Yes/No), if yes, specify
      - Reason (Results in death/ Is life threatening/ Leads to hospitalisation or prolongation of hospitalisation/ Causes persistent or significant disability or incapacity/ Causes a congenital anomaly or birth defect/ Is medically significant).
  - Subsequent treatments
    - Has the patient received any subsequent treatment? (Yes/No)
      - If yes, specify
        - Drug received
        - Starting dose
        - Treatment line
        - Start date

- End date
- Ongoing
- Best response attained (CR, PR, SD, DP/Not evaluable)
- Reason for discontinuation (DP/Toxicity/Other, specify)
- Vital status
  - Date of last follow-up
  - Status (Alive/Death)
    - If Death, specify
      - Date of death
      - Cause of death (DP, Other, specify)

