- Duration (months) of previous 1st-line treatment = (Date of end of 1st-line treatment – Date of start of 1st-line treatment) / 30.4375. If a patient is detected in whom this duration cannot be calculated or a negative time is left, it will not be considered in the descriptive analysis, and a list will be shown with the information related to this calculation of said patient.

- 
- Pre-treatment of 1st line: a descriptive table with the collected drugs will be shown (if necessary, a list will be sent to the sponsor for the grouping of these drugs). In addition, the registered drugs will be grouped into three groups: Sunitinib, Other iTK, and Others, and the descriptive table will be included in the report.
  - Duration (months) of previous 2nd-line treatment =  
 $(\text{Date of end of 2nd-line treatment} - \text{Date of start of 2nd-line treatment}) / 30.4375$ . If a patient is detected in whom this duration cannot be calculated or a negative time is left, it will not be considered in the descriptive analysis, and a list will be shown with the information related to this calculation of said patient.
  - Duration (months) of previous 3rd-line treatment =  
 $(\text{Date of end of 3rd-line treatment} - \text{Date of start of 3rd-line treatment}) / 30.4375$ . If a patient is detected in whom this duration cannot be calculated or a negative time is left, it will not be considered in the descriptive analysis, and a list will be shown with the information related to this calculation of said patient.
  - Duration (months) of previous 4th-line treatment =  
 $(\text{Date of end of 4th-line treatment} - \text{Date of start of 4th-line treatment}) / 30.4375$ . If a patient is detected in whom this duration cannot be calculated or a negative time is left, it will not be considered in the descriptive analysis, and a list will be shown with the information related to this calculation of said patient.
  - Duration (months) of previous 5th-line treatment or further =  $(\text{Date of end of 5th-line treatment} - \text{Date of start of 5th-line treatment}) / 30.4375$ . It will be analyzed only if there is an adequate sample (enough high) of patients with 5th or later previous lines.
  - Duration (months) of treatment with axitinib =  
 $(\text{Date of end of axitinib treatment or of latest follow-up if not suspended} - \text{Date of start of axitinib treatment}) / 30.4375$
  - Time (months) to increase or Time (months) to reduction of axitinib dose =  

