Risk groups are defined considering the following five factors (Favourable, Intermediate, Poor):

- ECOG/PS <1 (related to KPS <80)
- Time from first Diagnosis to Systemic Treatment less than 1 year
- LDH >1.5 x ULN
- Corrected calcium >10 mg/dl
- Haemoglobin < LLN

---

The risk groups are as follows:

- Favourable: 0 factors
  - Intermediate: 1 or 2 factors
  - Poor: >2 factors
- 
- Heng (or IMDC) risk group (described in appendix 11.1.). It will be analysed “at the beginning of the axitinib treatment” and “on the axitinib discontinuation”. These calculations will be performed on patients who have data on all the variables involved (in the case of a patient who does not have data on all the variables but has > 2 factors, it will be classified in the “Poor” risk group.

Risk groups are defined taking into account the following six factors (Low, Intermediate, High):

- ECOG/PS <1 (related to KPS <80)
- Time from first Diagnosis to Systemic Treatment less than 1 year
- Corrected calcium >10 mg/dl
- Haemoglobin < LLN
- Neutrophils > ULN
- Platelets > ULN

The risk groups are as follows:

- Favourable: 0 factors
  - Intermediate: 1 or 2 factors
  - Poor: >2 factors
- 
- Risk group according to MSKCC Criteria for patients previously treated with a TKI (defined in appendix 11.1). It will be analysed “at the beginning of the axitinib treatment”. Of note, all patients must have been previously treated with a TKI. These calculations will be performed on patients who have data on all the variables involved (in the case of a patient who does not have data on all the variables but has > 2 factors, it will be classified in the “Poor” risk group.

Risk groups are defined taking into account the following three factors (Low, Intermediate, High):

- ECOG/PS <1 (related to KPS <80)
- Haemoglobin < LLN
- Corrected calcium >10 mg/dl

The risk groups are as follows:

- Favourable: 0 factors
- Intermediate: 1 factor
- Poor: 2 or 3 factors
- The Objective Response Rate (ORR) is the frequency of subjects with CR or PR.
- The Clinical Benefit Rate is the frequency of subjects with CR, PR or SD.
- Increase of the axitinib dose to above 5 mg twice daily. Defined as having specified "Increase" at least one time, and in this case having specified "New dose" >5 mg/12h.
- Reduction of the axitinib dose to below 5 mg twice daily. Defined as having specified "Reduction" at least one time, and in this case having specified "New dose" <5 mg/12h.

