  - Baseline LDH levels  $>1.5 \times \text{ULN}$  (yes vs no). At the beginning of 1st line
  - Baseline Hgb levels  $\leq \text{LLN}$  (yes vs no). At the beginning of 1st line
  - Baseline corrected Ca++ levels  $>10$  mg/dl (yes vs no). At the beginning of 1st line
  - Baseline neutrophil levels  $> \text{ULN}$  (yes vs no). At the beginning of 1st line
  - Baseline platelet levels  $> \text{ULN}$  (yes vs no). At the beginning of 1st line
  - Smoking habits (smoker, non-smoker or former smoker). At the beginning of 1st line
  - Baseline LDH levels  $>1.5 \times \text{ULN}$  (yes vs no). At the beginning of axitinib treatment
  - Baseline Hgb levels  $\leq \text{LLN}$  (yes vs no). At the beginning of axitinib treatment
  - Baseline corrected Ca++ levels  $>10$  mg/dl (yes vs no). At the beginning of axitinib treatment
  - Baseline neutrophil levels  $> \text{ULN}$  (yes vs no). At the beginning of axitinib treatment
  - Baseline platelet levels  $> \text{ULN}$  (yes vs no). At the beginning of axitinib treatment
  - Smoking habits (smoker, non-smoker or former smoker). At the beginning of axitinib treatment

A logistic regression model will then be carried out to study the association between belonging to each of the two extreme treatment response groups, with each of the possible clinical factors of interest, prior to axitinib treatment. That is, those baseline factors (prior to the start with axitinib) that have been studied in section 7 and that are significant ( $P < 0.05$ ) or close to significance ( $P < 0.15$ ).

The factors in this situation will be summarized below, and that potential prognostic factors of the response to axitinib treatment (long responding group vs refractory group) are considered.

---

The optimal model of prognostic factors will be constructed with the variables that are finally significant ( $P < 0.05$ ).

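### SAP 7.1 tests ECOG and IMDC risk at the end of axitinib, and other values that arise after axitinib starts, as univariate factors for long response under an objective about baseline factors.

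*SAP*

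**What the plan says.** SAP 7.1 places the list under the primary objective and states that "an association analysis of the following factors with the study groups will be performed". The groups are long responders (PFS of at least 9 months) and refractory patients (best response to axitinib of PD).

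Two entries reach past the start of axitinib:

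- ECOG: "Baseline ECOG/PS and at the end of axitinib treatment", in categories 0, 1 and 2 or more.
- Risk group: "MSKCC (or IMDC) risk group in all moments in which it is analysed during the study". SAP 7 sets two time points for IMDC, the start of axitinib and "on the axitinib discontinuation".

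The source is a CRF block in SAP 6, "Risk criteria at discontinuation of treatment with axitinib". Stopping is itself a CRF question, "Has treatment with axitinib been discontinued? (Yes/No", and SAP 7 computes treatment duration from the "Date of end of axitinib treatment or of latest follow-up if not suspended". The SAP therefore expects some patients to be still on drug.

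For the logistic model, SAP 7.1 restricts candidates to "those baseline factors (prior to the start with axitinib") that reach P<0.05 or P<0.15. SAP 4 sets two-sided alpha at 0.05 for all tests, without multiplicity adjustment.

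**The concern.** A candidate factor for long response has to be known when axitinib starts. ECOG and IMDC risk at discontinuation are not. In refractory patients they will usually be recorded around progression, and in long responders usually after the 9-month mark. Patients who have not stopped contribute nothing. The test therefore compares condition at stopping, at different times and for possibly different reasons, in a subset that depends on how well the patient did.

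ECOG and IMDC risk are recognised prognostic factors, so a significant result in this list could easily be reported as a finding about who benefits from axitinib. The comparison cannot support that statement.

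**Working it through.** **Timing and availability.** The documents give no power or sample-size figure to reproduce, so the first step sets the passages side by side.

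| Item | Where | Known at axitinib start? | Who has it |
|---|---|---|---|
| ECOG at start of each line | Protocol 7.1 | Yes, up to and including the axitinib line | All, if recorded |
| ECOG at end of axitinib | SAP 7.1 only | No | Patients who stopped |
| IMDC at axitinib start | SAP 7 | Yes | Complete data, or more than 2 factors |
| IMDC at discontinuation | SAP 7, tested through 7.1 | No | Patients who stopped, with the same data rule |
| Neutrophil/lymphocyte ratio | SAP 7 and 7.1 | Yes; SAP 7 excludes discontinuation | All, if recorded |

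The protocol's factor list has no ECOG value at the end of axitinib. SAP 8 substitutes only incomplete dates, so an absent discontinuation value stays missing.

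**Patients who could be compared.** Protocol 8.5 and SAP 2.1 expect about 60 patients, and the protocol's study-population section a ratio of about 2:1. That gives 60 × 2/3 = 40 long responders and 60 × 1/3 = 20 refractory patients. The share *f* of long responders still on axitinib is not given. Assuming that every refractory patient stopped:

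| *f* (assumed) | Long responders with a value, 40 × (1 − *f*) | Refractory | Missing overall, 40*f*/60 |
|---|---|---|---|
| 0% | 40 | 20 | 0% |
| 10% | 36 | 20 | 6.7% |
| 25% | 30 | 20 | 16.7% |
| 50% | 20 | 20 | 33.3% |

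**What a p-value can pick up.** Suppose that baseline ECOG is unrelated to group, and that ECOG of 2 or more at stopping depends only on the reason for stopping. Its probability is *p* after progression and 0.15 otherwise. Let *t* be the share of long responders who stopped for a reason other than progression, and let all refractory patients stop for progression. The expected difference between groups is

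*p* − [(1 − *t*)*p* + 0.15*t*] = *t*(*p* − 0.15).

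It is zero at *t* = 0. At *t* = 0.4 it is 0.4 × 0.35 = 0.14 for *p* = 0.5, and 0.4 × 0.55 = 0.22 for *p* = 0.7. No baseline effect is involved.

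A simulation used 4,000 runs per setting, *f* = 10% or 25%, *p* = 0.5 or 0.7, and a two-sided Fisher test at 0.05 on ECOG of 2 or more. ECOG at axitinib start was set at 0.15 in both groups.

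| *t* (assumed) | Rejection, ECOG at stopping | Rejection, ECOG at axitinib start |
|---|---|---|
| 0% | 3-5% | 3-4% |
| 20% | 6-10% | 3-4% |
| 40% | 14-30% | 3-4% |
| 60% | 28-62% | 3-4% |

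The mix of reasons for stopping drives the excess. In this set-up the missing patients only reduce the numbers; any further selection from their absence is not modelled.

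**Other entries.** The same list contains suspension of axitinib, progression, best response to axitinib, duration of axitinib, further treatment and vital status. All arise after axitinib starts. Best response of PD defines the refractory group, so testing best response against group is circular.

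**The case against.** The strongest reply is that the SAP already separates the prognostic step. Only factors before axitinib start can enter the logistic model, and SAP 9.1 and 9.2 point back to 7.1, where that limit stands. A reader might infer that the final model is contaminated. The documents do not support this, although 9.1 and 9.2 would be clearer if they repeated the limit.

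Four other readings go further than the text allows:

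- **That the values always follow the outcome, or come at least 9 months in.** PFS runs to progression, death or last follow-up, not to the end of treatment. A patient who stopped early for toxicity and still reached 9 months without progression has a value from before that mark. It is nonetheless post-baseline.
- **That nearly all refractory patients have a value.** The CRF allows Unknown, the data come from charts, Protocol 9.1 expects many patients to have died, and IMDC needs all components unless more than two factors are present.
- **That error rates are certainly inflated.** If nearly all stopping is for progression, the simulation shows little or no excess.
- **That the word Baseline in the ECOG entry is itself the fault.** The three ECOG entries share that wording and each names its time point.

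It can also be said that the study is exploratory and states no hypotheses, that the list may be a general between-group table, and that SAP 9.1 reports total and valid percentages, so missing values will be visible. These points lower the stakes. They do not make the comparison interpretable: the list is introduced as an analysis of factors under the primary objective, and its tests are run at 0.05.

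**Conclusion.** The point holds for the univariate association tests in SAP 7.1. ECOG at the end of axitinib and IMDC risk at discontinuation are post-baseline, exist only for patients who stopped, and cannot show which patients were likely to become long responders. The other entries that arise after axitinib starts share the first defect, most plainly best response.

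The documents do not fix the size. The share still on axitinib, the mix of reasons for stopping and the ECOG probabilities are all assumptions. Over the range examined, the chance of a nominally significant ECOG result at stopping, with no baseline effect, runs from 3-5% to 28-62%. The upper end needs 60% of the long responders who stopped to have done so for a reason other than progression. This is a moderate fault of interpretation that should be corrected.

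**What to change.** - In SAP 7.1, apply the existing limit for the logistic model, values at or before axitinib start, to the whole association list. Repeat it in 9.1 and 9.2.
- Replace the all-time-points wording for risk group, and the three ECOG entries, with first-line start and axitinib start only.
- Report ECOG and IMDC at discontinuation by group among patients who stopped, with N and reason for stopping, and without a p-value.
- Move suspension, progression, best response to axitinib, duration of axitinib, further treatment and vital status to descriptive tables by group, without tests in this list.

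The cost is SAP wording. No data are lost, no new data are needed, and fewer tests are run. SAP version 3 followed a draft of results, so any p-values for these items already produced should be left out of the primary-objective findings.
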